3.2 Study Endpoints

3.2.1 Primary Study Endpoints

The primary endpoint will be overall change in WAB-AQ between the first baseline visit and the 12 week follow-up (real tDCS compared to sham tDCS).

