3.1 General Design

This is a double-blind, sham-controlled, crossover study. Groups will be counterbalanced according to PPA subtype. All participants will undergo baseline language testing and neuroimaging prior to receiving 10 treatment sessions over 2 weeks (Monday-Friday) of either real or sham tDCS paired with mCILT. Immediate post-treatment, 6 week and 12 week follow-ups will be obtained. Participants will then crossover into the second portion of the study whereby they will receive the opposite treatment protocol (real or sham tDCS + mCILT) and an additional 24 week follow-up. Treatment must take place within 2 days to 4 weeks of baseline testing. The overall timeline for each subject's participation is indicated below in Figure 1.

Figure 1: Timeline for each subject

Enrollment	Baseline MRI	Baseline 1	Baseline 2	Treatment	Follow-up	Follow-up MRI	6 week Follow-up	12 week Follow-up	12 week Follow-up MRI	
SCREENING	VISIT 1**	VISIT 2*	VISIT 3*	Visit 4-13	VISIT 14*	VISIT 15**	VISIT 16*	VISIT 17*	VISIT 18**	
- Informed Consent - Screening Forms - Demographics Form	MRI	-CCRSA -WAB 1 -CILT 1 -NWRT -LTROG Oral -PPT Picture -NACC Word Reading -NACC Sentence Repetition	-WAB 2 -CILT 2 -PRT -DDK -LTROG Written -PPT Words -Story -NACC Sentence Reading	tDCS mCILT OR Sham tDCS mCILT	+	- WAB - CILT - NWRT - PRT - LTROG Oral & Written - PPT Picture & Words - NACC Word reading, Sentence Reading & Repetition - DDK - CCRSA - Story	MRI	- WAB - CILT - NWRT - PRT - LTROG Oral & Written - PPT Picture & Words - NACC Word reading, Sentence Reading & Repetition - DDK - CCRSA - Story	-CCRSA -WAB 1 -CILT 1 -NWRT -LTROG Oral -PPT Picture -NACC Word Reading -NACC Sentence Repetition	MRI
~ 1 hour	~ 1 hour	~ 3 hrs	~ 3 hrs	~ 1.5 hrs	~ 3 hrs	~ 1 hour	~ 3 hrs	~ 3 hrs	~ 1 hour	

CONFIDENTIAL

Crossover Baseline	Crossover Treatment	Crossover Follow-up	Crossover Follow-up MRI	Crossover 6 week Follow-up	Crossover 12 week Follow-up	Crossover 12 week Follow-up MRI	Crossover 24 week Follow-up
VISIT 19*	VISIT 20-29	VISIT 30*	VISIT 31**	VISIT 32*	VISIT 33*	VISIT 34**	Visit 35

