-WAB 2 -CILT 2 -PRT -DDK -LTROG Written -PPT Words -Story -NACC Sentence Reading	tDCS + CILT OR Sham tDCS + CILT	- WAB - CILT - NWRT - PRT - LTROG Oral & Written - PPT Picture & Words - NACC Word reading, Sentence Reading & Repetition - DDK - CCRSA - Story	MRI	- WAB - CILT - NWRT - PRT - LTROG Oral & Written - PPT Picture & Words - NACC Word reading, Sentence Reading & Repetition - DDK - CCRSA - Story	- WAB - CILT - NWRT - PRT - LTROG Oral & Written - PPT Picture & Words - NACC Word reading, Sentence Reading & Repetition - DDK - CCRSA - Story	MRI	- WAB - CILT - NWRT - PRT - LTROG Oral & Written - PPT Picture & Words - NACC Word reading, Sentence Reading & Repetition - DDK - CCRSA - Story
~ 3 hours	~ 1.5 hours	~ 3 hours	~ 1 hour	~ 3 hours	~ 3 hours	~ 1 hour	~ 3 hours

* Depending on patient's schedule / fatigue levels, language assessment visits may be accomplished over two to three visits instead of one. To reduce burden of extra visits, language assessments may also be completed at day 1 treatment, prior to the start of the treatment itself.

**Depending on patient's schedule / fatigue levels, MRI visits may be combined with another visit.

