6.4.5 Visit 18 (12 week Follow-up MRI)

Subjects will undergo an MRI scan on a 3T Siemens unit; no contrast will be administered.

The anticipated time of this visit is 1 hour.

Depending on patient's schedule / fatigue levels, MRI visits may be combined with follow-up language testing.

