6.4.6 Visits 19-35 (Crossover)

Participants will crossover into the second half of the study after the 12 week follow-up. Visits 18 & 19 will serve as Baseline and then all study procedures will exactly match the first half of the study. The crossover will include an additional follow-up visit at 24 weeks.

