7.6 Efficacy Evaluations

No interim analyses for efficacy are planned, as previous work suggests that the maximal benefit is likely to be obtained at the 12 week endpoint and there is no additional risk to the subject after the tDCS is completed.

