8.1 Primary Endpoint

The primary endpoint will be overall change in WAB-AQ between the baseline visit and the 12 week follow-up visit (real compared to sham tDCS).

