8.4 Statistical Methods

8.4.1 Treatment Effect on Language Performance

A linear mixed-effects model will be used to determine whether the change in performance induced by tDCS + mCILT for subjects in each PPA variant group differs significantly from that induced by sham stimulation, covarying for age, sex, education and disease duration at time of study if they are imbalanced between the two groups at baseline. The mixed model will include a fixed effect for sequence, period, treatment, and the interaction between treatment and period. A random intercept term will be included in the mixed-effects model to account for correlations from repeated outcome measures. Additional analyses will examine change in other language battery tests, and exploratory analysis will examine baseline aphasia severity as a predictor of response.

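### The period 2 WAB-AQ baseline conflicts between sections with no carry-over assumption stated, and the 8.4.1 model lists one aliased fixed effect

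*Combined protocol and SAP*

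**What the plan says.** Three sections define the baseline of the primary endpoint differently.

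- Section 3.2.1: "overall change in WAB-AQ between the first baseline visit and the 12 week follow-up (real tDCS compared to sham tDCS".
- Section 8.1: "overall change in WAB-AQ between the baseline visit and the 12 week follow-up visit (real compared to sham tDCS". The word first is gone, and no period is named.
- Section 6.4.6, on the crossover: "Visits 18 & 19 will serve as Baseline and then all study procedures will exactly match the first half of the study". Section 6.4.5 heads one of these two visits "Visit 18 (12 week Follow-up MRI".

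Figure 1 shows the same battery at Visit 2 and Visit 17 ("CCRSA -WAB 1 -CILT 1 -NWRT -LTROG Oral -PPT Picture") and a second battery at Visit 3 and Visit 19 ("WAB 2 -CILT 2 -PRT -DDK -LTROG Written"). It labels Visit 17 as the 12-week follow-up and Visit 19 as the crossover baseline. Section 7.5 requires two WABs before treatment but does not say how to combine them.

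On timing, section 6.4.6 places the crossover after the 12-week follow-up, and section 7.6 says that "previous work suggests that the maximal benefit is likely to be obtained at the 12 week endpoint". Section 1.1.2 reports pilot benefit lasting up to twelve weeks. No washout or carry-over assumption appears anywhere.

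On the model, section 8.4.1 states: "The mixed model will include a fixed effect for sequence, period, treatment, and the interaction between treatment and period". A random intercept is added. The purpose of the interaction is not given, and no contrast is named as primary.

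**The concern.** In a two-period crossover, the change score in period 2 depends on where it starts. If real tDCS still has an effect when a real-first participant enters period 2, a baseline taken then contains part of the treatment effect, while the baseline at study entry does not. The plan allows both readings, so the same data can give two different primary estimates, and the choice could be made after the results are known.

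The model adds a second ambiguity. A two-sequence, two-period design has four cell means. The listed terms with the intercept ask for five parameters. What the coefficient labelled treatment means then depends on which term the software drops and how it codes the factors.

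The 5-point responder rule in 8.4.2 inherits the baseline problem. It names no baseline, and its models list no period term.

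**Working it through.** The plan gives no figure on baseline or carry-over to reproduce. Its 25 subjects per variant group (8.3) come without an effect size or SD, and 25 is used below only as a sample size.

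**1. Rank of the model.** Take one week 12 change per period and 0/1 coding (sequence = 1 for sham-first, period = 1 for the second period, treatment = 1 for real).

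| Cell | Intercept | Sequence | Period | Treatment | Treatment x period |
|---|---|---|---|---|---|
| Real-first, period 1 | 1 | 0 | 0 | 1 | 0 |
| Real-first, period 2 | 1 | 0 | 1 | 0 | 0 |
| Sham-first, period 1 | 1 | 1 | 0 | 0 | 0 |
| Sham-first, period 2 | 1 | 1 | 1 | 1 | 1 |

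In every row, sequence = 1 - period - treatment + 2(treatment x period). So there are five columns of rank four.

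- The period-averaged contrast, treatment + 0.5(interaction), is estimable. The treatment coefficient alone is not.
- Dropping the interaction makes the treatment coefficient the period-averaged contrast. Dropping sequence under this coding makes it the period 1 between-subject contrast.
- Three visits per period with visit effects leave the same single deficiency (seven columns, rank six).
- Because the interaction is aliased with sequence, it cannot isolate carry-over.

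**2. Expected estimate by baseline.** Let T be the true 12-week effect, d the share present at Visit 19 and p the share present at Visit 33 (the second week 12 visit). Effects are taken as additive, with 0 <= p <= d <= 1. Both shares are assumptions. In real-first participants, Visit 33 falls at least 12 + 2 + 12 = 26 weeks after real stimulation ended.

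Cell means, apart from period effects: sham-first, 0 then T; real-first, T then pT (Visit 2 baseline) or (p - d)T (Visit 19 baseline).

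- Visit 2: [(T - 0) + (T - pT)]/2 = T(1 - p/2)
- Visit 19: [(T - 0) + (T - (p - d)T)]/2 = T(1 + (d - p)/2)
- Gap: dT/2

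| d | p | Visit 2 | Visit 19 |
|---|---|---|---|
| 0 | 0 | 1.00T | 1.00T |
| 0.5 | 0 | 1.00T | 1.25T |
| 0.5 | 0.25 | 0.875T | 1.125T |
| 0.5 | 0.5 | 0.75T | 1.00T |
| 1 | 0 | 1.00T | 1.50T |
| 1 | 0.5 | 0.75T | 1.25T |
| 1 | 1 | 0.50T | 1.00T |

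The errors are -pT/2 and +(d - p)T/2, so Visit 19 is closer to T only when p > d/2. If T = 0, both estimates are zero on average.

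For a mean of Visits 17 and 19, the period 2 baseline holds a share (1 + d)/2. The estimate is then T(1 + ((1 + d)/2 - p)/2), which is T(1 + d)/4 above the Visit 2 value.

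**3. Precision.** Assume independent unit-variance errors at each visit and a person-specific slope per period with SD s = 0, 0.5 or 1. The period 1 baseline is the mean of Visits 2 and 3, except under the common Visit 2 reading. Variance of the within-person difference between the two period changes:

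- Visit 19: 1 + 0.5 + 1 + 1 = 3.5
- Visits 17 and 19 mean: 2.25 + 0.5 + 1 + 0.25 = 4.0, because Visit 17 enters with weight 1.5
- Visit 2 for both periods: the baseline cancels, leaving 2 + s^2 = 2.0, 2.25 or 3.0

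Relative to a common Visit 2 baseline, Visit 19 multiplies the variance by 1.75, 1.56 or 1.17. If the former had 80% power for a given effect, the latter would have about 56%, 61% or 74% for the same effect (for example, Phi(2.80/sqrt(1.75) - 1.96) = 56%).

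**4. Type I error of the random intercept.** Null simulation in this error model: 25 subjects (13 and 12), 40,000 runs, intercept variance bounded at zero, t reference with 23 or 46 df.

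| Period 2 baseline | s = 0 | s = 0.5 | s = 1 |
|---|---|---|---|
| Visits 17 and 19 mean | 8-9% | 7% | 5% |
| Visit 19 | 6% | 5% | 5% |

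With the pair, the shared Visit 17 score gives the two changes a correlation of -0.5/1.5 = -0.33 at s = 0. A random intercept cannot represent a negative correlation. An unstructured covariance restores about 5%.

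**5. Responder rule.** If Visit 2 is the baseline throughout, change on real tDCS spans about 2 + 12 = 14 weeks in real-first participants and at least 2 + 12 + 2 + 12 = 28 weeks in sham-first participants, against the same 5-point cut in a progressive disease.

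**The case against.** The strongest reply is that the documents can be read coherently. The baseline phase in 3.1.2 includes an MRI, and Visit 1 is that scan. The crossover has no other pre-treatment MRI, so Visit 18 can be its baseline scan and Visit 19 its baseline WAB. The word first in 3.2.1 may only separate Visit 2 from Visit 3. Section 8.5 analyses the whole randomised crossover population, which points to a contrast over both periods, and software will fit the model by dropping a term.

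Much of this stands, and it rules out several stronger readings that a reader might infer:

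- *That 6.4.6 is simply wrong because Visit 18 is an MRI.* The reading above is the most coherent one.
- *That the Visit 17 and 19 pair is the intended baseline.* No section names Visit 17 as a baseline. The inference rests on Figure 1's labels and the two-WAB statement in 7.5. Figure 1's partial batteries also disagree with 6.2.3 and 6.4.4, which describe the full battery at Visits 3 and 17. The pair is possible, no more.
- *That Visit 19 is the correct choice and costs nothing.* It is less precise than a common Visit 2 baseline, and it inflates the estimate when d > p.
- *That carry-over invalidates the test.* It does not bias the test of zero effect.

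The reply does not remove the conflict. Sections 3.2.1 and 8.1 never mention a period-specific baseline, and 6.4.6 does not say that it governs the primary endpoint. Listing an aliased interaction is not a carry-over assumption.

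**Conclusion.** The point holds in two parts. The rank deficiency is certain: it follows from the design alone, and the treatment coefficient has no fixed meaning until a term is dropped. The baseline conflict is in the text. Its effect on the estimate is dT/2 between the Visit 2 and Visit 19 readings, from nothing at d = 0 to half the true effect at d = 1.

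The size rests on additive effects and on d and p, which the documents do not give. The values 0.5T and 1.5T are extremes under different baselines and different persistence, and no single analysis spans them. The Visit 2 reading is conservative; the Visit 19 reading overstates the effect when d > p. The documents do not settle which is preferable. The precision and type I error figures depend on the stated error model. They do not show that the trial is underpowered, since no SD or effect size is given.

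This should be fixed, and it can be done in wording.

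**What to change.** 1. In 8.4.1, drop treatment-by-period, keep sequence, period and treatment, and name the week 12 treatment coefficient as the primary contrast.
2. Reconcile 3.2.1, 8.1, 6.4.6 and Figure 1 to one stated WAB-AQ baseline per period before unblinding, including how the two pre-treatment WABs are combined. Use the same baselines for the 5-point rule in 8.4.2.
3. If Visit 17 enters the period 2 baseline, replace the random intercept by an unstructured covariance for the two period changes.
4. State the carry-over assumption, and report the baseline-adjusted period 1 contrast with its interval as a supportive, carry-over-free estimate.

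The cost is endpoint and SAP wording plus one analysis of data already planned. Two downsides should be disclosed. First, the baseline choice trades bias against variance, so it is the sponsor's to make and justify. Second, the period 1 contrast is imprecise. With equal variances and between-period correlation r, its SE is sqrt(2/(1 - r)) times the crossover SE: 1.4 at r = 0 and 2.0 at r = 0.5. In the error model above with a Visit 19 baseline, the ratio is sqrt(4(1.5 + s^2)/3.5), or 1.3 to 1.7. It should support the primary result and not replace it.

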6.2.3 Visit 3 (Baseline 2)

Subjects will repeat full language battery from Visit 2 for reliability.

Testing is anticipated to take about 3 hours; however if the session is too long for the participant it is possible to split the visit in two.

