7.5 Other Evaluations, Measures

The following battery of language tasks will be administered prior to treatment and at 6 weeks and 12 weeks (& 24 weeks in crossover) after the completion of tDCS: (1) The Western Aphasia Battery (WAB; Shewan & Kertesz, 1980) samples a number of different language functions and

CONFIDENTIAL

generates a summary score between 0-100 (Aphasia Quotient, AQ), interpretable as general aphasia severity. The WAB will be administered on two occasions prior to treatment to obtain a stable baseline. Word and non-word repetition tests from the Moss Psycholinguistic Aphasia Database (MAPPD; Dell et al, 1997; Sobel, Brecher, & Schwartz, 2006) will be used to further assess lexical and post-lexical phonological encoding. Word repetition will also be used to quantify instances of consonant distortion, prosodic alteration, and other features of speech apraxia. The Pyramids and Palm Trees test (Picture version; Howard & Patterson, 1992) will be used to assess core semantic memory. (5) The Communication Confidence Rating Scale for Aphasia (Babbitt, Cherney, & Halper, 2008) will be administered to assess changes in quality of communication in daily life. Spontaneous Speech as an indicator of functional communication will be assessed with the Cinderella story (Stark, 2010). The Linguistics Test for Reception of Grammar (LTROG, Bishop, 1989) will be administered to assess grammatically comprehension of speech and written language. Finally, 2 pre-treatment baselines will be obtained on the stimuli used for CILT. We note that the baseline sessions may require more than one day to complete.

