8.3 Sample Size and Power Determination

To calculate power, we started from an ambitious but realistic estimate of the population available at the participating recruitment sites. We intend to recruit 62 subjects, although 25 subjects will be adequate to detect a difference between real and sham stimulation within each group (alpha = 0.05; power = 0.8). Although our historical attrition rate has been 15%, we will conservatively anticipate a 25% attrition rate and will therefore enroll 31 subjects in each PPA variant arm.

CONFIDENTIAL

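### The primary WAB-AQ change starts from the first of two pre-treatment readings, which leaves avoidable test-retest error in period-1 change scores, and the period-2 baseline reading is not clearly named

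*Combined protocol and SAP*

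**What the plan says.** - **Primary endpoint, section 3.2.1:** "overall change in WAB-AQ between the first baseline visit and the 12 week follow-up (real tDCS compared to sham tDCS".
- **Primary endpoint, section 8.1:** "overall change in WAB-AQ between the baseline visit and the 12 week follow-up visit (real compared to sham tDCS". Two baseline visits are scheduled, and this wording does not say whether the first, the second or their mean is meant.
- **Why the WAB is given twice, section 7.5:** "The WAB will be administered on two occasions prior to treatment to obtain a stable baseline". Section 6.2.3 adds, of Visit 3: "Subjects will repeat full language battery from Visit 2 for reliability".
- **Crossover baseline, section 6.4.6:** "Visits 18 & 19 will serve as Baseline". Section 6.4.5 and Figure 1 make Visit 18 an MRI visit. The WABs nearest the crossover are at Visit 17, which is the period-1 12-week outcome, and at Visit 19, where Figure 1 lists "WAB 2 -CILT 2 -PRT -DDK".
- **Analysis, sections 8.4.1 and 8.4.2:** the mixed model has sequence, period, treatment and treatment-by-period terms with a random intercept. How baseline enters it is not stated. The responder outcome is a 5-point WAB-AQ change, again without saying from which reading. Baseline severity is a candidate predictor.

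Nothing in the document gives the Visit 3 WAB a role in the primary endpoint.

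**The concern.** The plan collects a second pre-treatment WAB so that the baseline will be stable, then words its main endpoint so that this reading is not used. A single reading passes its full test-retest error into the change score. Visit 2 is also the first WAB in the study, so any gain from first exposure to the test would appear as period-1 improvement.

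Four uses of the data are exposed:
- **The responder call.** It is made on one person's change, so nothing averages out. Its covariates in section 8.4.2 are age, disease duration and sex, without period or sequence. With period-specific baselines, a first-exposure gain would help people given real tDCS first to reach 5 points.
- **Baseline severity as a predictor.** If one noisy reading is both the predictor and part of the change, a low first score by chance looks like a good response.
- **Subjects with only one period.** Section 8.3 anticipates 25% attrition and section 8.5 analyses the full randomized population. For these subjects the baseline error cannot cancel.
- **The real-versus-sham contrast,** depending on which reading anchors period 2.

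Because sections 3.2.1, 8.1 and 6.4.6 do not agree on the baseline, an analyst could also choose among readings after seeing the data.

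**Working it through.** **Inputs.** WAB readings at Visits 2 and 3 (pre-treatment), 17 (period-1 12-week outcome), 19 (crossover baseline) and 33 (period-2 12-week outcome), from Figure 1 and sections 6.2 to 6.4. The labels WAB 1 and WAB 2 in Figure 1 are taken as first and second administrations, in line with section 7.5. Let s2 be the test-retest error variance of one WAB-AQ, independent between readings. The documents give no value for it.

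**The plan's own figure.** Section 8.3 says "25 subjects will be adequate to detect a difference between real and sham stimulation within each group (alpha = 0.05; power = 0.8". It cannot be reproduced, because no effect size or standard deviation is given. Taken at face value (two-sided 0.05, 2x2 crossover, 23 degrees of freedom), n = 25 implies a standardised within-subject difference of about 0.585. That value is used below only to express variance changes as power.

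**Step 1: period-1 change score.**
- From Visit 2 alone: s2 + s2 = 2*s2.
- From the mean of Visits 2 and 3: s2 + s2/2 = 1.5*s2.
- Reduction: 0.5/2 = 25% of the error part. The error variance of baseline severity itself halves, from s2 to s2/2.

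**Step 2: real-versus-sham contrast.** This is the period-1 change minus the period-2 change. Its error variance is s2 times the sum of squared weights on Visits 2, 3, 17, 19 and 33.

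| Period-1 baseline | Period-2 baseline | Weights | Error variance |
|---|---|---|---|
| Visit 2 | Visit 19 | -1, 0, 1, 1, -1 | 4*s2 |
| Mean of 2 and 3 | Visit 19 | -0.5, -0.5, 1, 1, -1 | 3.5*s2 |
| Visit 2 | Visit 17 | -1, 0, 2, 0, -1 | 6*s2 |
| Mean of 2 and 3 | Visit 17 | -0.5, -0.5, 2, 0, -1 | 5.5*s2 |
| Mean of 2 and 3 | Mean of 17 and 19 | -0.5, -0.5, 1.5, 0.5, -1 | 4*s2 |
| Visit 2 | Visit 2 | 0, 0, 1, 0, -1 | 2*s2 |
| Mean of 2 and 3 | Mean of 2 and 3 | 0, 0, 1, 0, -1 | 2*s2 |

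- Visit 19 anchor: 3.5/4 = 0.875, so the standard error is 6.5% lower (sqrt(0.875) = 0.935).
- Visit 17 anchor: 5.5/6 = 0.917, so the standard error is 4.3% lower (sqrt(0.917) = 0.957).
- Common anchor: no change in completers.

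Visit 17 costs more because the same score is both the period-1 outcome and the period-2 baseline, so it enters with weight 2.

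**Step 3: dilution.** Suppose there is also genuine occasion-to-occasion variation t2, shared by readings taken close together, and let rho = s2/(s2 + t2). With Visit 19 the contrast variance goes from 4*s2 + 6*t2 to 3.5*s2 + 6*t2. For rho = 0.25, 0.5, 0.75 and 1 the ratio is 0.977, 0.950, 0.917 and 0.875. If n = 25 gave 80% power before, it gives 81%, 82%, 83% and 85% after. With Visit 17 the ratio is 1 - rho/12, at best 0.917, or 83% power.

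**Step 4: responder call, as an illustration.** Assume no true change, normal errors, and error SD s. The chance of an apparent 5-point gain in period 1 is P(Z > (5 - shift)/SD). SD is s*sqrt(2) with one baseline and s*sqrt(1.5) with the mean. A first-exposure gain g shifts the change by g with Visit 2 alone and by g/2 with the mean.

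| Assumed s | g = 0, one reading | g = 0, mean | g = 2, one reading | g = 2, mean |
|---|---|---|---|---|
| 2 | 3.9% | 2.1% | 14.4% | 5.1% |
| 3 | 11.9% | 8.7% | 24.0% | 13.8% |
| 4 | 18.8% | 15.4% | 29.8% | 20.7% |

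Both s and g are assumptions.

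**The case against.** **The single anchor is not settled.** Only section 3.2.1 says first. Section 8.1 is open, section 6.4.6 names two crossover visits, and section 8.4.1 leaves room for both readings to be modelled. A reader might infer that the Visit 3 reading is certain to be discarded. The documents do not go that far. What they show is an endpoint that names one reading, a statistical section that names none, and no text that uses the second.

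**The contrast need not suffer.** A reader might infer that a single baseline always adds noise to real versus sham. In a crossover it does not: if Visit 2 anchors both periods, it cancels in every completer. This stands as a limit on the point, although section 6.4.6 gives the crossover period its own baseline. The small variance in the last two rows of the Step 2 table does not by itself argue for a common anchor, because period-2 change would then also span the period-1 treatment and follow-up.

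**A larger gain is not on offer.** A reader might also suppose that averaging in both periods would cut the contrast's error variance to 3*s2, a 25% reduction. That needs two independent pre-treatment WABs in period 2. Figure 1 schedules only Visit 17, already the period-1 outcome, and Visit 19. Averaging both available pairs gives 4*s2, no better than Visits 2 and 19 alone.

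**First-exposure gain is unproven.** The documents give no evidence for it, and with a common Visit 2 anchor it would enter both changes equally. The order argument is therefore conditional. The reduction in error variance does not depend on it.

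**Precision would differ by period.** With a two-reading mean in period 1 and Visit 19 alone in period 2, responder calls carry 1.5*s2 for people given real tDCS first and 2*s2 for those given it second. This is a fair cost and should be stated in the plan.

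**Conclusion.** The point holds as a modest but real weakness. Section 3.2.1 uses one of two readings collected for a stable baseline, and sections 3.2.1, 8.1 and 6.4.6 do not together identify the baseline for each period.

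The firm part is the period-1 change score: averaging removes 25% of its test-retest error variance. That benefit reaches the responder call, baseline severity and single-period subjects. It rests on independent errors of equal variance at Visits 2 and 3.

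The contrast part is conditional: 12.5% of the error variance with Visit 19, 8.3% with Visit 17, and nothing in completers with a common anchor. In power terms, 80% becomes at most about 85%, and less if much of the within-subject variation is genuine fluctuation. The actual gain in WAB-AQ points cannot be given, because neither s2 nor any first-exposure gain is in the documents. Nothing here shows that the treatment comparison is biased.

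**What to change.** 1. In sections 3.2.1 and 8.1, use the same sentence: the period-1 baseline is the mean of the Visit 2 and Visit 3 WAB-AQ, or the available score if one is missing.
2. In the same place, name the period-2 baseline reading. Visit 19 is preferable to Visit 17, because Visit 17 is also the period-1 outcome.
3. Reconcile section 6.4.6 with Figure 1. If Visits 18 and 19 are meant as the MRI baseline and the language baseline respectively, say so.
4. Use these baselines for the 5-point responder definition and for baseline severity in sections 8.4.1 and 8.4.2, state how baseline enters the mixed model, and note that the responder call is more precise in period 1 than in period 2.

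The cost is a few sentences. All the readings are already scheduled, so no visits, tests or patients are added.
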